**d. Justification of why participants will not receive routine care or will have current therapy stopped.**

Participants will continue to receive routine care for their multiple sclerosis.

**e. Justification for inclusion of a placebo or non-treatment group.**

While this trial is primarily focused on establishing the safety and tolerability of TUDCA in patients with progressive MS, the inclusion of a placebo group will enable us to determine whether changes observed in serum bile acid profiles, gut microbiota, immunophenotype and clinical/ quality of life measures are related to TUDCA treatment. This would provide information regarding the utility of pursuing larger trials focused on clinical outcomes in this patient population.

**f. Definition of treatment failure or participant removal criteria.**

Patients selected for the study will be removed if they:

- 1) They develop abnormal safety labs as defined below
- 2) Develop a serious adverse event
- 3) Inform us that they became pregnant during the study
- 4) Are unable to follow the requirement of the study
- 5) Request to be removed

**g. Description of what happens to participants receiving therapy when study ends or if a participant's participation in the study ends prematurely.**

The subject's medical care will continue unaltered when the study ends or if a subject is removed from the study.

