## 7. Study Statistics

**a. Primary outcome variable.**

The primary outcome of this study is the safety and tolerability of TUDCA supplementation. This will be based on number of adverse events occurring in the two treatment groups and the rate of drop-out in each study arm. This data will be documented at each study visit.

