**c. Statistical plan including sample size justification and interim data analysis.**

Safety data will be analyzed as they are captured in real time. Assessments will focus on AEs (including study treatment tolerability assessments, laboratory evaluations, vital signs and physical examination). The incidence rate of AEs will be recorded by system organ class, severity and by relationship to study treatment. Tolerability analysis will be based on the number (%) of participants who failed to complete the study due to adverse events. Lab values for each parameter will be summarized by shift tables. For quantitative parameters, we will present summary statistics for actual values and change from baseline. We will compare changes over the 16-week treatment period between the groups using mixed effects regression analyses to account for repeated measures using random subject-specific intercepts and slopes.

Metabolomics data will be analyzed at the end of the study following quantitation of the 15 bile acids included in our panel. Summary statistics will be used to characterize these outcomes. We will then assess normality of these measures and perform appropriate univariate testing to determine which bile acids are significantly altered by TUDCA supplementation. A mixed effects longitudinal model will also be used to test which bile acids are altered between visits across the two groups. Models will also adjust for important covariates including BMI, age, gender and measures derived from the food frequency questionnaire.

Gut microbiota data, *a priori* analyses will assess changes in relative abundances of different gut bacteria as well as microbial genes that encode bile acid metabolizing enzymes (identified from the literature and NCBI Gene database) which occur as a result of TUDCA treatment. Exploratory analysis will assess the effects of TUDCA on the metagenome using a combination of pathway and set-based approaches previously applied in metagenomics analysis of MS and other diseases to identify other biologically relevant changes[41]–[43].

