#### **d. Early stopping rules.**

We will discontinue treatment if a participant develops abnormal safety labs (serum AST or ALT > 3 x upper limit of normal, serum bilirubin > 3 x upper limit of normal, eGFR < 60ml/min/1.73m^2), becomes pregnant during the study, cannot tolerate the drug, develops an adverse event grade 3 or higher that is possibly related to study treatment or wants to discontinue treatment. Any death that is at least possibly related to the study will put the study on hold. The Data and Safety Monitoring Board will determine if it is safe to resume the study. Subjects who become suicidal during the study (codes 1-4, <http://www.fda.gov/downloads/Drugs/GuidanceComplianceRegulatoryInformation/Guidance/UCM225130.pdf>) will be referred to a psychiatrist or to a psychiatric emergency room for evaluation at the discretion of the site treating physician.

Data and Safety Monitoring Board (DSMB): An independent DSMB will be utilized for subject monitoring. The DSMB will consist of a neurologist, a hepatologist and a statistician. The DSMB will meet every 12 weeks and any time an SAE occurs. All SAEs will be reported to the DSMB delegates within 24 hours of the study staff becoming aware of the SAE. The DSMB will be required to review SAEs and respond with recommendations within two business days. If more than 3 subjects experience serious adverse events, the study will be put on hold and the DSMB will decide on whether the adverse events were secondary to study treatment. They will make a judgement as to whether the study should continue and, if so, whether a reduction in TUDCA dosing or other protocol modifications are recommended.

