### c. Plan for reporting unanticipated problems or study deviations.

Unexpected Adverse Event: An adverse event is considered unexpected when its nature or severity is not consistent with the product information (e.g. package insert safety information, the investigational plan, the investigator's brochure, the protocol, or the informed consent form).

Serious Adverse Event: A serious adverse event (any adverse event that suggests a significant hazard, contraindication, side effect, or precaution) must be reported. This includes, but may not be limited to, death, a life-threatening event, inpatient hospitalization or prolongation of existing hospitalization, persistent or significant disability/ incapacity, congenital anomaly/ birth defect, other protocol-specified conditions, or an event that requires intervention to prevent permanent impairment or damage. Serious adverse events will be collected from informed consent signing until 30 days after study completion or until 30 days after a participant withdraws from the study.

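### Section 4f removes participants from the study for abnormal safety labs, any SAE or pregnancy where Section 7d only stops treatment; read literally, it leaves no week-16 safety follow-up after removal at week 8

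*Combined protocol and SAP*

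**What the plan says.** Section 4f opens with "Patients selected for the study will be removed if they" and lists five conditions. The first is "They develop abnormal safety labs as defined below"; the second is any SAE, with no requirement that it be related to the drug; the third is pregnancy. Section 4g shows what removal means: the subject's "medical care will continue unaltered when the study ends or if a subject is removed from the study".

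The laboratory limits that Section 4f points to are given only in Section 7d: AST or ALT above 3 times the upper limit of normal, bilirubin above 3 times that limit, or eGFR below 60. There the consequence differs: "We will discontinue treatment if a participant develops abnormal safety labs". The same sentence applies that consequence to pregnancy and to possibly related events of grade 3 or worse. The pregnancy text in Section 8c also has the participant stop the medication, and follows the pregnancy to its outcome.

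The primary outcome (Section 7a) is the count of adverse events by arm and "the rate of drop-out in each study arm". Section 7c adds: "Tolerability analysis will be based on the number (%) of participants who failed to complete the study due to adverse events". For quantitative safety parameters it says "We will compare changes over the 16-week treatment period between the groups", using a mixed model. Section 8c collects SAEs "until 30 days after a participant withdraws from the study".

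**The concern.** The plan gives two answers on whether a participant who meets a safety trigger stays in follow-up. Site staff reading Section 4f would end participation. Staff reading Section 7d would stop the capsules and, as nothing there cancels later visits, would presumably still see the participant at week 16.

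Safety is the primary outcome, and the people concerned are those with a safety signal. What may be lost is whether a liver or kidney abnormality resolved, persisted or worsened off drug, together with their week-16 safety data. That bears on their care, on planning a larger trial, and on the DSMB's task under Section 7d of judging whether events were caused by treatment and whether the dose should change.

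**Working it through.** **The plan's own figure.** Section 7c needs up to 27 per arm and allows 10% drop-out: 27 / (1 − 0.10) = 30 per arm. This reproduces. The allowance is 0.10 × 30 = 3 participants per arm.

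**The two rules side by side.**

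| Trigger | Sections 4f and 4g | Section 7d |
|---|---|---|
| AST/ALT, bilirubin or eGFR beyond limits | out of the study | stop treatment |
| Pregnancy | out of the study | stop treatment (Section 8c agrees) |
| SAE, possibly related, grade 3 or worse | out of the study | stop treatment |
| SAE, unrelated or below grade 3 | out of the study | not in itself a reason to stop |

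For laboratory values and pregnancy only the consequence differs. For SAEs the trigger differs too, because seriousness (Section 8c definition) and CTCAE grade are separate scales.

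**What is still collected after removal.** Section 8c covers SAEs for 30 days (taking withdrawal to include removal by the investigator) and pregnancy outcome. Section 4g continues medical care, but no text brings its laboratory values into the trial data. The unscheduled visit in Section 4b names neither laboratory tests nor a period after removal. The schedule has no early-termination or off-treatment visit, and nothing asks for an abnormal test to be repeated until it resolves.

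**Size per participant removed at week 8.** Post-baseline panels are scheduled at weeks 8 and 16.
- Panels without provision: 1 of 2.
- Non-serious adverse event collection without provision: 16 − 8 = 8 of 16 weeks.
- SAE window: removal on day 8 × 7 = 56; window closes on day 56 + 30 = 86; the week-16 visit is day 16 × 7 = 112; gap 112 − 86 = 26 days.

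Removal on a week-16 value loses no scheduled visit.

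**Size per arm of 30.** The documents give no expected number of removals, so 1, 2 and 3 are illustrations only: 1/30 = 3.3%, 2/30 = 6.7% and 3/30 = 10% of week-16 panels.

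**Checks on the remedy.** If the same 1, 2 or 3 people stay in follow-up and drop-out is not redefined, recorded drop-out falls by 3.3, 6.7 or 10 percentage points. At the plan's own 10% (3 of 30) it could fall to 0%. This would be a side effect of a careless fix, not a harm in the present plan. Likewise, a participant whose value rises by D at week 8 and is back at baseline by week 16 adds D/30 to the arm's mean change at week 8 and 0 at week 16. Shift tables built on the worst post-baseline value keep D.

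**The case against.** The strongest reply is that this is one rule worded loosely. Section 4f's heading combines treatment failure with removal, its laboratory item defers to limits set out in Section 7d where the action is to stop treatment, and Section 8c treats pregnancy the same way. That is plausible, but Section 4g speaks expressly of removal from the study, so the literal reading cannot be dismissed. If the intention was one rule, clarification costs little.

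A second reply is that safeguards exist: adverse event assessment includes laboratory evaluations, the unscheduled visit responds to events, SAEs are collected for 30 days, and a DSMB that includes a hepatologist meets every 12 weeks and at any SAE. This stands in part. None of it provides a week-16 panel after removal.

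A third reply is that stopping on any SAE is a defensible conservative choice in an early safety trial. This stands. Narrowing Section 4f to Section 7d's grade and relatedness test would remove the automatic stop for a possibly related SAE below grade 3 and for any SAE judged unrelated. The inconsistency can be cured without that.

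A reader might infer that the primary comparison is biased or that all safety follow-up ends at removal. The documents support neither: the triggering event and value count in the outcome and enter the model, and SAEs and pregnancies remain covered for the periods shown. Nor does Section 7d expressly require later visits; it merely does not cancel them. The ALS trial described in the Background cannot settle how many removals to expect: its arm sizes are not given, it ran for 54 weeks, and it reports laboratory changes in general rather than these limits.

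**Conclusion.** The point holds in a limited form and should be corrected. Sections 4f and 4g conflict with Section 7d on whether a participant with a safety trigger remains in the study. If Section 4f is followed literally, a participant removed at week 8 has no provision for the week-16 panel or for the last 8 weeks of non-serious adverse events.

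The between-arm comparison is little affected and the trial's validity is not in question. The loss is information on the course of a safety signal after the drug is stopped. The size rests on removal taking effect at the week-8 visit (day 56) and on Section 4f prevailing over Section 7d in practice. The number affected is probably small and is not estimable from the documents.

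**What to change.** 1. **Section 4f.** Keep every existing trigger, including any SAE. For the laboratory, SAE and pregnancy triggers, change the consequence from removal from the study to discontinuation of study drug. Add any SAE to the list in Section 7d so that the two sections agree.
2. **Section 7d.** State that participants who stop drug keep the remaining scheduled adverse event assessments and safety labs through week 16 unless they withdraw consent, and that a triggering abnormal test is repeated until stable or resolved.
3. **Sections 7a and 7c.** Count discontinuation of study drug as drop-out, and discontinuation because of an adverse event as tolerability failure, whether or not follow-up continues. Retention then cannot lower the recorded drop-out rate.
4. **Section 7c.** Count all adverse events through week 16 in the primary number, each flagged as on or off drug. Base shift tables on the worst post-baseline value and flag off-drug laboratory values. Recovery then does not mask a signal, and later worsening is not set aside in a separate table.

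The cost is a wording amendment to Sections 4f, 7a, 7c and 7d. The week-16 visit and panel are already scheduled. The downside is a few extra chemistry panels for repeat tests, and some participants who stop drug will decline further visits.

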**5. Inclusion/Exclusion Criteria**

The inclusion and exclusion criteria for participants in this trial are listed in the table below.

Eligibility criterion	Rationale
Diagnosis of Progressive MS based on Lublin criteria	We are focusing on people with PMS since they are more likely to have low bile acid levels
Age ≥ 18 years	To include only adults in the trial
On the same therapy for the past 6 months and not expected to switch therapy in the next 6 months	To avoid confounding by changes in immunomodulatory therapy during the trial
No relapse in the past 3 months	To avoid any confounding introduced by relapse
Exclusion criterion	Rationale
No previous history of liver disease	Confounding due to decreased bile acid production or altered bile acid metabolism
No stage IV/V chronic kidney disease or other severe metabolic derangements	To reduce risk of adverse effects or confounding due to other systemic disorders
BMI < 15 kg/m  and BMI > 40 kg/m 	Reduce confounding due to extremes of BMI
Female patients who are pregnant or nursing, or not	Prevent potential teratogenicity

willing to use contraception	
Chronic antibiotic use	Prevent confounding of microbiome analyses
Corticosteroid treatment within the past 30 days	Prevent confounding of treatment effect
Known history of other neuroinflammatory, neurodegenerative or systemic autoimmune disease	These diseases could require other treatments or be affected by the trial medication.
No current or prior history of the following – 
 
• Bariatric surgery
 
• Small intestinal surgery resulting in loss of length of the jejunum or ileum
 
• Chronic diseases of the small intestine (e.g., Crohn’s Disease, gluten sensitive enteropathy, or other disorders that could lead to malabsorption)
 
• Abnormal bile duct anatomy
 
• Sclerosing cholangitis
 
• Anti-mitochondrial antibodies
 
	These conditions could alter bile acid handling in the gut or bile acid levels in circulation

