#### 1. Abstract

People with multiple sclerosis have abnormalities in multiple metabolic pathways that can be identified using metabolomics. The **aberrant pathways identified in people with MS, in our preliminary studies using untargeted metabolomics**, include **primary and secondary bile acid metabolism**. Bile acids have several biological functions beyond aiding in lipid absorption in the gut, and can modulate the function of cells in the peripheral immune system and the CNS. Bile acid metabolism is also closely linked to the gut microbiota. **Bile acid supplementation reduced neuroinflammation and was neuroprotective** in models of various neurodegenerative and neuroinflammatory disorders. Bile acid supplementation has been tested in early trials in neurodegenerative disease and has been well tolerated. Whether bile acid supplementation is beneficial in MS is not known.

The objective of this study is to test the **safety and tolerability of supplementation with a bile acid – tauroursodeoxycholic acid (TUDCA) in people with progressive MS**. We will also assess whether this intervention normalizes the abnormal bile acid levels in circulation and impacts the composition of the gut microbiota and peripheral immune cell function.

Aims:

1. Establish the safety of bile acid supplementation and determine whether this intervention leads to normalization of the bile acid profile in people with MS with abnormal bile acid metabolism
2. Assess the effects of bile acid supplementation on the gut microbiota and the peripheral immune system in people with MS

There is a need for adjunctive treatments that carry low risk and address the underlying pathophysiology of MS. This project aims to show that a bile acid – TUDCA is safe and well-tolerated in MS patients and could result in beneficial effects on bile acid metabolism, gut microbiome and peripheral immune cell function in people with MS. If successful, this project could yield a new treatment strategy with both immunomodulatory and neuroprotective effects.

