#### 2. Objectives

##### Primary Objectives

**Aim 1. Establish the safety and tolerability of bile acid supplementation and determine whether this intervention leads to normalization of the bile acid profile in people with progressive MS with abnormal bile acid metabolism**

*Hypothesis: Bile acid supplementation is safe and tolerable and will help normalize the bile acid profile in people with MS.*

**Method:** In a randomized, double-blind, placebo-controlled, phase 1/2 study of bile acid supplementation in people with progressive MS with abnormal bile acid metabolism, we will establish the safety and tolerability of this intervention and evaluate its effects on bile acid profiles as determined by targeted metabolomics.

**Aim 2. Assess the effects of bile acid supplementation on the gut microbiota and the peripheral immune system in people with MS**

*Hypothesis: Bile acid supplementation leads to alterations in the gut microbiota and peripheral immune system in people with MS.*

[figure not shown]
**Method:** We will determine the change in gut microbiota composition following bile acid supplementation and determine changes in peripheral immune cell function in participants enrolled in the phase 1/2 trial of bile acid supplementation mentioned in Aim 1.

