## PRELIMINARY DATA

**People with MS have alterations in their metabolome compared to healthy controls.** We performed untargeted global metabolomic profiling of plasma from people with RRMS and healthy controls (n=27 in each group) utilizing gas or liquid chromatography coupled with tandem mass spectrometry. The mass spectra obtained were compared to a reference library to identify individual compounds and the relative abundance was calculated using the area under the curve of the mass spectra. Using this method, we identified over 600 metabolites in the plasma of study participants and were able to differentiate the two groups based on their metabolic profiles using a statistical model optimized for high-dimensional datasets - orthogonal partial least squares -discriminant analysis (OPLS-DA) (Figure 2).

[figure not shown]
**People with MS have alterations in both primary and secondary bile acid metabolism.** In the first discovery cohort described above we noted reductions in the levels of multiple primary and secondary bile acids in people with MS. To follow-up on our findings, we performed untargeted metabolomics in a validation cohort of 50 RRMS, 50 progressive MS and 50 healthy controls. In this study we again noted a reduction in multiple bile acids in RRMS and PMS groups (Figure 3A). We also investigated alterations in individual metabolic pathways using pathway dysregulation scores (calculated as described in Drier et al)[28]. This method generates a score for a metabolic pathway for each individual based on their distance from a principal components curve constructed based on healthy control data. These scores range from 0 to 1 with higher scores representing greater abnormality in the pathway. We found significant alterations in both primary and secondary bile acid metabolism in RRMS and PMS groups (Figure 3B & 3C). In this cohort, we also noted a correlation of PDS scores for secondary bile acid metabolism with those for xenobiotic

[figure not shown]
**Figure 2. Metabolomics differentiates people with MS from healthy controls.** The plot depicts the first two components from an orthogonal partial least squares -discriminant analysis (OPLS-DA) model. The two groups can be clearly distinguished in this plot.

metabolism (Xanthine and Benzoate,  $p < 0.01$  for both) indicative of a link between the gut microbiota and bile acid metabolism.

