Since pathway analysis utilizes *a priori* specification of metabolic pathways, we also used an agnostic method - weighted correlation network analysis (WGCNA) that identifies modules of highly correlated metabolites. We identified a module that contained bile acids and the eigen-metabolite values for this module differed significantly between RRMS, PMS and control groups with a reduction noted in bile acids in both RRMS and PMS groups ( $p < 0.001$  for both).

[figure not shown]

**In animal-models of MS supplementation with bile acids leads to improvement of disease.** We then tested the hypothesis that supplementation with a bile acid (TUDCA) would alter the course of disease in a mouse model of MS - EAE. Seven-week old C57/BL6 mice were immunized with MOG35-55 and CFA subcutaneously along with injection of pertussis toxin intraperitoneally (IP). Mice were then monitored for development of disease, and at disease onset they were randomized to either TUDCA 500 mg/kg or placebo (PBS) IP for 3 weeks. At the end of the experiment we noted a significant reduction in the severity of disease in the TUDCA treated group (Figure 4A) and a reduction in spinal cord demyelination (based on Black-gold staining) and macrophage infiltration (Iba1+ cells) on histology (Figure 4B). Recent studies from other groups corroborate our findings; Ho & Steinman demonstrated that supplementation with a synthetic bile acid resulted in reduction in severity of EAE[29]. Additionally, another independent group demonstrated the ability of a FXR agonist to reduce CNS inflammation through an IL-10 mediated pathway[15].

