**Metabolomics can be used to monitor the effects of therapeutic interventions on the metabolome.**

We utilized metabolomics to assess the effect of vitamin D supplementation on the metabolome in people with MS and healthy controls. In this study, 24 people with MS and 27 controls received 5000 IU of vitamin D daily for 3 months. We obtained plasma at beginning and end of the study and performed metabolomic profiling. We utilized WGCNA to identify metabolite modules and then utilized generalized estimating equations (GEE) to determine the change in metabolite modules following vitamin D treatment.

**Figure 5. Metabolomics identifies the effects of vitamin D supplementation of oxidative stress and lipid metabolism.** Panel A is a circos plot displaying contents of two metabolite modules that were altered by vitamin D supplementation – red module containing lipids and green module containing oxidative stress related metabolites. Panel B shows change in the green module (redox homeostasis) derived from a GEE model with a change noted in healthy control group but not in the MS group (p=0.006 for interaction).

We found a reduction in markers of oxidative stress and alterations in lipid metabolism in healthy controls following vitamin D supplementation but noted a lack of a similar effect in people with MS (Figure 5).

This study demonstrated the ability of metabolomics to track changes in metabolic pathways following a therapeutic intervention.

[figure not shown]
These preliminary data clearly demonstrate that people with MS have altered bile acid metabolism and that supplementation of a bile acid (TUDCA) had a beneficial effect in an animal model of MS. Additionally, we demonstrate that metabolomics can be used to monitor the effects of a therapeutic intervention in MS.

We hypothesize that bile acid supplementation in people with MS will be safe, well tolerated and lead to normalization of the bile acid profile and favorable immune and neuroprotective effects

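### Aim 1 asks about normalising bile acids in people whose bile acids are abnormal, but participants are not selected on that and the analysis has no healthy reference, so it can show change or a rise against placebo, not normalisation

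*Combined protocol and SAP*

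**What the plan says.** **The aim.** Section 2 (Objectives, Aim 1) sets out to "determine whether this intervention leads to normalization of the bile acid profile in people with progressive MS with abnormal bile acid metabolism". The Method under that aim describes the trial population in the same restricted way. The Abstract says "We will also assess whether this intervention normalizes the abnormal bile acid levels in circulation", and the preliminary data close with the hypothesis that supplementation "will be safe, well tolerated and lead to normalization of the bile acid profile".

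**The population.** The criteria table in Section 5 requires progressive MS, adult age, stable therapy, no recent relapse and the listed exclusions. Its only link to bile acids is a rationale: "We are focusing on people with PMS since they are more likely to have low bile acid levels". The screening visit list and procedure table in Section 4a include blood counts, a metabolic panel, HbA1c, lipids and a pregnancy test, but no bile acid assay.

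**The evidence of abnormality.** It is at group level: "We found significant alterations in both primary and secondary bile acid metabolism in RRMS and PMS groups", and a module analysis "with a reduction noted in bile acids in both RRMS and PMS groups". A pathway score per person, from 0 to 1 with higher meaning more abnormal, was calculated "based on their distance from a principal components curve constructed based on healthy control data". That score is not named as a trial outcome.

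**The analysis.** Section 7b says fasting plasma will show whether the drug raised acids found deficient in MS. Section 7c quantifies 15 acids once the study is over, tests univariately which are altered, and fits a longitudinal mixed model across the two groups. The trial is sized for a 50 to 70% change in one acid.

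**The concern.** Normalisation has two parts: a starting point outside the healthy range and movement toward that range. The plan secures neither. Abnormality is not established in the individuals enrolled, and the analysis contains nothing against which movement toward health could be measured.

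The gap is sharper here because the study drug belongs to the class of compounds being measured. A rise in TUDCA, or in acids derived from it, would be expected simply because participants took the capsules. Section 3 also notes that the composition of the pool can matter when its total size does not change, so a higher level cannot be equated with a normal one.

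At stake is what may be concluded. A positive bile acid result could be reported as support for the normalisation half of Aim 1 when it had tested something weaker. Section 4e says the placebo comparison of these measures is meant to inform whether larger trials are worth pursuing, so the distinction has consequences.

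**Working it through.** **1. Population, side by side**

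| Place | Population |
|---|---|
| Section 2, Aim 1 and its Method | Progressive MS, bile acid metabolism abnormal |
| Section 4a, design | Progressive MS meeting the criteria |
| Section 5, criteria | No bile acid level or score |
| Section 4a, screening list and table | No bile acid assay |
| Section 7c | Panel quantified after the study ends |

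The last row means that the panel cannot have been used to select participants.

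**2. Question against analysis.** The question is normalisation. Section 7c tests alteration; Section 7b adds an upward direction for deficient acids. Neither names a healthy reference, an upper limit, or an analysis of those abnormal at baseline.

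**3. The plan's own sample size.** Inputs from Section 7c: 14 to 27 per arm, 85% power, two-sided 0.05, 10% drop-out.
- Drop-out: 27 / 0.9 = 30 per arm, as stated.
- Detectable standardised difference (two-sample t test): 0.831 at 27 per arm, 1.177 at 14 per arm.
- Implied SD: 0.50 / 0.831 = 0.602 and 0.70 / 1.177 = 0.595.

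Both ends of the range fit one SD of about 60% of the reference level. The sizing is internally consistent, and it is sizing for change in one acid.

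**4. Why a rise is not evidence of normalisation.** Section 6a cites a 1.9 to 8 fold change in total serum bile acids with UDCA or TUDCA (2 to 8 fold in Section 7c). Suppose this is a rise, which is an assumption. Let b be the baseline as a fraction of healthy and F the fold rise. On a log scale the total ends nearer to healthy only if |ln(bF)| < |ln b|, that is, b < 1/√F.
- F = 1.9: b < 0.73.
- F = 8: b < 0.35.

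The text gives no participant-level baseline relative to healthy, so this does not say how many would move closer. It shows only that a rise can be movement toward or away from normal.

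**5. Could a distance-from-healthy endpoint answer the question at this size?** Assumptions: lognormal levels; CV 60% (the SD from step 3, used as a between-person CV); placebo stays at 67% of healthy; TUDCA ends exactly at healthy with the same spread. The measure is the mean absolute z-score on the log scale.
- Log SD = √ln(1 + 0.6²) = 0.555. Starting offset = ln(1/0.667) / 0.555 = 0.73 SD.
- One acid: the mean of |z| is 1.00 at an offset of 0.73 and √(2/π) = 0.80 at zero, so even healthy people do not score zero. The SDs of |z| are √(1 + 0.73² − 1.00²) = 0.73 and √(1 − 0.80²) = 0.60, pooled 0.67. Difference = 0.20 / 0.67 = about 0.3 SD.
- Ten acids correlated 0.5 (simulation): about 0.5 SD.

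| Scenario, 27 per arm | Power |
|---|---|
| One acid, from 67%, unadjusted | about 20% |
| Ten acids, from 67%, unadjusted | about 43% |
| Ten acids, from 67%, adjusted, pre-post correlation 0.5 to 0.7 (assumed) | about 54% to 70% |
| Ten acids, from 59%, unadjusted | about 78% |

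Even full correction could be missed, so such a comparison is suitable only as an exploratory addition.

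**The case against.** The strongest defence is that the formal commitment is soft. The hypothesis under Aim 1 says only that supplementation will help normalise the profile, in people with MS generally. The Method promises to evaluate effects on bile acid profiles, which Section 7c does. Section 7b goes further than asking which acids move, because its question about deficient acids is directional and rests on the earlier comparisons with controls. Enrolling unselected progressive MS is a legitimate enrichment choice, and the rationale in Section 5 is not itself an error. Bile acids are a secondary outcome in a study whose primary outcome is safety and tolerability.

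Most of this stands and limits the point to a mismatch of aim, population and analysis. It does not remove the mismatch: the Aim 1 heading, the Abstract and the closing hypothesis of the preliminary data all speak of normalisation, and the Aim 1 Method itself describes the population as having abnormal bile acid metabolism.

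A reader might infer more than the documents support:
- *That overshoot past healthy would count as success.* No section sets a bile acid success criterion, so this cannot be said.
- *That many participants will have normal bile acids.* The text does not give the share. The design diagram and the figure comparing progressive MS with controls were not available here, so part of that uncertainty comes from the copy. A hidden screening step is unlikely, given when the panel is quantified.
- *That a 50 to 70% rise is predicted and would carry people past normal.* Those figures are a detectable change, not a forecast.
- *That the sample size is wrong.* Step 3 finds no error.

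**Conclusion.** The point holds as a should-fix. Followed exactly, the plan can support a statement that TUDCA changes, or raises, bile acids versus placebo in progressive MS. It cannot support a statement that TUDCA normalises them, nor one about people with abnormal bile acid metabolism as a defined group. For TUDCA and its metabolites, a change is mainly evidence of exposure. For other acids it would be evidence of a drug effect, but still not of a return to normal.

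This conclusion rests on the text alone: no bile acid criterion or screening assay, end-of-study quantitation, and no reference in the analysis. The calculations in steps 4 and 5 are illustrations under stated assumptions and are not needed for it. The primary outcome in Section 7a is untouched. Plasma before and after treatment and a placebo arm are planned, so the wording and analysis can still be aligned before unblinding.

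**What to change.** 1. **Reword the Aim 1 population** as progressive MS not selected on individual bile acid levels. Limit the bile acid conclusion to a between-arm change versus placebo, unless a healthy reference is pre-specified before unblinding. Carry the same wording into the Abstract and the closing hypothesis of the preliminary data.
2. **Separate exposure from effect.** Name in advance TUDCA and those of its metabolites that are on the panel (for example UDCA and GUDCA, if included) and report them as exposure. Base any statement about correcting deficient acids on the other acids, also listed in advance.
3. **Optional.** If a healthy-control reference on the same targeted assay and under comparable fasting conditions already exists, pre-specify one week 16 between-arm comparison of distance from it. Adjust for the pre-dose value (baseline, or the screening research draw under the three-visit option), report a confidence interval, and label it exploratory with the power caveat above.

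**Cost.** Items 1 and 2 are wording and reporting changes; they need no new samples or participants. Item 3 is analysis work only if the reference exists. The preliminary control data may not serve, because in that work "the relative abundance was calculated using the area under the curve of the mass spectra", and the documents do not show that suitable fasting control plasma is available. The downside is a narrower stated aim and conclusion.
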